1 BACKGROUND AND RATIONALE

1.1 Introduction

Antenatal education classes were developed to inform expectant mothers about pregnancy, labour and birth as well as the postpartum period with the aim of improving the pregnancy and childbirth experience (Ahldén et al., 2012; Ip et al., 2009). Conceptually, they were based, for example, on the pioneering work of Lamaze (1956) and Grantly Dick-Read (1944) (Svensson et al., 2009). Studies indicate positive emotional effects of antenatal education classes on labour and birth outcomes. This includes lower levels of fear of childbirth, lower rates of caesarean birth at the women's request, a higher rate of spontaneous births, a stronger involvement of the partner, better chances of initiating breastfeeding, and a lower likelihood of developing depression symptoms during the postpartum period (Ip et al., 2009; Rouhe et al., 2013; Svensson et al., 2008). However, a standardized, evidence-based education program is missing. There is limited evidence on the link between birth preparation and neonatal outcomes (Shand et al., 2022).

1.2 Background

Today, women and their partners are offered antenatal education classes during pregnancy, which in Switzerland are partly financed by the health insurance. In most cases, the courses are offered by midwives and consist of a series of sessions starting in the second trimester of pregnancy. They are usually weekly courses over 6-10 evenings or weekend courses over two to three days. However, the content of antenatal classes vary widely, as does the focus and the start and duration of the program. The goal of the classes offered today is to increase knowledge and confidence in relation to pregnancy, labour and birth as well as the postpartum period (Ricchi et al., 2019), especially through information and preparation in managing labour pain through skilled techniques (Shand et al., 2022). Therefore, antenatal education classes, which focus on breathing and relaxation techniques, offer an optimal opportunity to prepare for labour and birth and the pain management.

Exercising breathing and relaxation techniques frequently and intensively before childbirth improves the feasibility of using them during birth. This leads to beneficial effects such as increased coping with labour pain and increased self-efficacy (Byrne et al., 2014). Women felt more in control as they were able to use the trained skills appropriate to their individual needs, which consequently increased their ability to feel in control, as well as being able to manage their own labour and birth (Howarth & Swain, 2019a). Self-efficacy is an important concept in labour and birth management when women want to feel confident that they will be able to maintain control during labour by managing their labour pain (Ip et al., 2009).

In maternity care, practices around birth preparation are based on experience, but they have hardly been systematically developed, implemented, and evaluated (Nolan, 2009). Although several studies have shown positive effects on self-efficacy, lower rates of epidural anaesthesia and the memory of labour pain (Abbasi et al., 2018; Bergström et al., 2009; Duncan et al., 2017; Howarth & Swain, 2019b; Levett et al., 2016; Miquelutti et al., 2013; Pan et al., 2019) the important role of self-efficacy in women's ability to cope with labour and birth has hardly been integrated into the development of antenatal education classes (Ip et al., 2009). Moreover, evidence of a potential relation between antenatal education classes and neonatal outcomes has been hard to identify so far (Gluck et al., 2020; Shand et al., 2022; Vanderlaan et al., 2022; Yohai et al., 2018).

The best available evidence for the impact of antenatal classes is from research with women who fear childbirth. For this group of women, a group psychoeducation course paired with skilled breathing and relaxation techniques had a positive effect on the women's pregnancy outcomes and childbirth experience (Ryding et al., 2018). Antenatal education classes focusing on breathing and relaxation techniques is thereby assumed to strengthen the resources of women with increased fear of childbirth and enable them to act competently and proactively during childbirth. In line with this argument, studies have shown that women who fear childbirth, especially first-time mothers, benefit from the relieving effects of breathing and relaxation on labour pain and

anxiety, (Salmela-Aro et al., 2012). Building on this recent evidence, we assume that antenatal education classes may also positively influence maternal and neonatal birth outcomes in women without heightened fear of childbirth. We therefore intend to conduct an antenatal education class focusing on a breathing and relaxation technique and assess the impact of such a class on self-efficacy, as well as other maternal and neonatal birth outcomes.

2 STUDY OBJECTIVES AND DESIGN

2.1 Hypothesis and primary objective

The following hypothesis was formed for the BreLax study:

- Women who attend an antenatal education class that include training in breathing and relaxation techniques show significantly higher self-efficacy rates than women in a standard antenatal education class that does not include training in breathing and relaxation techniques.

The main objective of the study is therefore to evaluate the effectiveness of antenatal education classes that include a breathing and relaxation technique, in relation to maternal and neonatal outcomes.

2.2 Primary and secondary endpoints

The primary objective is to compare the effects of antenatal education that includes a breathing and relaxation technique on self-efficacy before, during, and after birth to a standard antenatal education class without a focus on breathing and relaxation techniques and after birth.

In this study, self-efficacy is defined as follows. Self-efficacy is a person's own belief that he or she is able to cope with difficult situations and challenges on his or her own (Bandura, 1977). This means women are confident and believe that they can cope with birth by themselves.

The secondary objectives are:

- (2) To identify the impact of BreLax on maternal outcomes: women's satisfaction with their childbirth experience, self-control, pain management, mobility during labour, duration of labour and fetal attachment.
- (3) To analyse the effects of BreLax on neonatal outcomes: 5-minute Apgar-Score and arterial umbilical cord pH.
- (4) To determine women's perceptions of the acceptability and applicability of the learned breathing and relaxation techniques before and during labour.
- (5) To assess the feasibility and effectiveness perceptions of the birth attending midwives regarding the intervention.

As background variables and potential covariates factors such as mother's sociodemographic data (e.g., age, family type, education, and occupation), the presence of chronic diseases as well as perinatal factors will be assessed. Correspondingly, relevant newborn indicators such as gestational age or birth weight will be measured.

2.3 Study design

The study will be conducted as a population-based randomised controlled trial (RCT) with a pre-post design and two parallel-arms: The intervention arm is an antenatal education class that includes a breathing and relaxation technique. The control arm is an antenatal education class that is like the one in the intervention arm but does not include a breathing and relaxation technique.

As quantitative pre-post outcome measures, mothers will fill in two validated questionnaires before and after birth:

- German version of the Childbirth Self-Efficacy Inventory (CBSEI-32) (Schmidt et al., 2016)
- German version of the Childbirth Experience Questionnaire (CEQ-2) (Pedersen et al., 2021).

Complementary, using a qualitative method approach, birth attendant midwives' perceptions on the feasibility and practicability of including the breathing and relaxation intervention in antenatal education classes will be assessed in semi-structured interviews.

2.4 Study intervention

It is recommended to start attending antenatal education in the second trimester. This applies to both the intervention and the control group. The women and their partners will be randomly assigned to one of two groups. One group serves as control group (standard care) and will receive a standard antenatal education class without a breathing and relaxation technique and exercises while the other group will receive antenatal education plus the designed intervention of a breathing and relaxation technique and exercises (BreLax: intervention group). Both groups receive information on labour and birth and the postpartum period.

The developed multicomponent intervention is based on the theoretical concept of Bandura's self-efficacy theory (1977). According to Bandura (1977), self-efficacy is considered to be the expectation of whether an individual is capable of performing a particular behaviour in a given situation, which can be divided into outcome expectation and self-efficacy expectation. Outcome expectations refer to the individual's prediction of the possible outcomes of a set of behaviours. If someone predicts that a certain behaviour would lead to a certain outcome, that behaviour may be activated and chosen. Self-efficacy is primarily influenced by four sources of information, namely performance, vicarious experience, verbal persuasion and physiological and emotional states (Bandura, 1977).

According to Bandura (1997), a strong belief in one's own ability to exercise some control over one's physical condition can serve as a psychological prognostic indicator of the likely level of health functioning (Ip et al., 2009). In line with these assumptions, self-efficacy has been shown to have an important influence on how labour is perceived and physically endured ([name] et al., 2022). Therefore, we assume that any strategy that reduces and/or controls distractions during birth such as emotional tension, can increase self-efficacy. Consequently, breathing and relaxation techniques are predicted to improve women's self-efficacy beliefs as they contribute to the control and reduction of distractions that hinder birth.

In order to increase women's self-efficacy beliefs that they trust themselves to be able to manage the birth process, the BreLax intervention will use all four sources of self-efficacy improving information. Women will experience that they can successfully perform the breathing and relaxation techniques and see that similar other can do it, too. They will also perceive reassuring comments from the class instructors and will feel less distractible emotions and physical arousal.

The core of the breathing technique is prolonged exhalation and with a certain number of repetitions and amplitudes (Evans, 2014). Such techniques have been taught for many years in antenatal education and are actively supported by many midwives during labour and birth. In the present study, the focus is on prolonged exhalation with an individual rhythm, which is learned and practised by the women during antenatal education. In addition, the women will be encouraged to continue practising at home with the help of a manual.

The main advantage of this technique is to be prepared for labour and birth, use it actively even in stressful situation, to learn an individual breathing pattern and to relax comfortably. Breathing technique means breathing with a certain number of repetitions and amplitudes (Evans, 2014).

2.4.1 Breath awareness (BA)

Breath awareness provides physical, mental and emotional control. Deep breathing increases blood circulation, oxygen flow and reduces stress, which benefits both mother and baby. By learning conscious breathing and relaxation techniques, women can learn to control themselves when uterine contractions start, control their pain and relax, which boosts their confidence (Irmak Vural & Aslan, 2019).

- Exercises to learn prolonged exhalation (following the 3-6 breathing technique for relaxation)
- Exercises for mental and physical relaxation (4 upright positions, standing, sitting, 4-foot, elevated lateral position)
- Optional: visualisation, music

Figure 1 Standing Position ©BreLax

Figure 2 4-Feet Position @BreLax

Figure 3 Sitting Position ©BreLax

Figure 4 Lying Position ©BreLax

Women need to learn to use their breathing individually. Breathing and relaxation techniques are only useful and practical if women can try them out and apply them in different everyday situations. Breathing and relaxation techniques can be used on any day and in any stressful or uncomfortable situation (Doriana et al., 2010). For this reason, it is important that women continue to practice at home. In the best case, the breathing and relaxation techniques become a kind of routine or become so automated that the techniques are remembered during birth and can be used accordingly. For a kind of habit to form, it is necessary for women to practice over a period of time (Mazar & Wood, 2018). Previous literature shows that an average of 66 days is required to recall automated exercises (Gardner et al., 2020). This time period coincides optimally with the recommended start of the antenatal education class in the second trimester.

2.4.2 Informational component

The intervention and the standard care aim to inform women about pregnancy, labour and birth and the postpartum period. The main difference is that the intervention group focuses on the element of a breathing and relaxation technique (See Table 1). Midwives instruct the participants on how to do the exercises, how to perform the breathing patterns and how to assume the respective positions and movements. In addition, the women receive a manual to practice at home. The control group receives the standard care.

Table 1 Content of classes

Content.	BreLax-Model (intervention)	Standard care (control)
Pregnancy		
Nutrition	✓	✓
Infections	✓	✓
Being pregnant / Doing pregnancy	✓	✓
Labour and birth		
Labour and birth	✓	✓
Complications	✓	✓
Non-pharmalogical medications	✓	✓
Pharmalogical medications	✓	✓
BreLax intervention	✓	x
Partner support	✓	✓
BreLax Handout	✓	x
BreLax web-application	✓	x
Postpartum		
Baby food	✓	✓
Baby care	✓	✓
Attachment	✓	✓
Sleep	✓	✓
New Role as a mom/dad	✓	✓

3 STUDY POPULATION AND STUDY PROCEDURES

3.1 Inclusion and exclusion criteria, justification of study population

Inclusion and exclusion criteria are defined for the randomized controlled trial as well as the individual interviews with midwives after birth.

The quantitative data collection:

- Inclusion criteria:
 - pregnant women with a singleton low-risk pregnancy
 - receiving antenatal care
 - being willing to attend an antenatal education class and planning a vaginal birth at the Canton Hospital Winterthur
 - ≥ 18 years old
 - sufficient oral and written German language knowledge

- Exclusion criteria:
 - women, who plan an elective caesarean section
 - pregnant with multiples
 - younger than 18 years old
 - do not have sufficient oral and written German language knowledge

The criteria for the individual interviews with the birth attendant midwives are that the midwife must have supported the woman for a minimum of 60 minutes and that she has sufficient written and oral German language skills.

3.2 Recruitment, screening and informed consent procedure

Women will be recruited via the Cantonal Hospital Winterthur and midwives in antenatal care at the hospital, surrounding gynaecological practices and midwifery practices will be informed about the study and will receive flyers for circulation in the institutions. Midwives and doctors will hand out a flyer with information about the study and the call for interested women to contact the study leader at ZHAW. Contact information of interested women will only be provided to the study leader of ZHAW after women explicitly agreed and prefer to be contacted.

The investigator will explain to each participant the nature of the study, its purpose, the procedures involved, the expected duration, the potential risks and benefits and any discomfort it may entail. Each participant will be informed that the participation in the study is voluntary and that she may withdraw from the study at any time and that withdrawal of consent will not affect her subsequent medical assistance and treatment.

The participant will be informed that her medical records about their birth will be examined by authorised individuals other than their treating obstetrician.

All participants for the study will be provided a participant information sheet and a consent form describing the study and providing sufficient information for participants to make an informed decision about their participation in the study. All potential participants will receive at least 24 hours to decide whether to participate or not.

The formal consent of a participant, using the approved consent form, will be obtained before the participant is submitted to any study procedure. The consent form will be signed and dated by the investigator simultaneously or after participants signature according to possibility. As this is a study of the risk category A and not all potential participants have scheduled visits in the hospitals, oral information can also be provided by telephone by the investigator. The study information and consent form in these cases will be sent by mail post and the participant will sign first and send back the consent form. In order not to put pressure on the women, the investigator will only sign after the signed consent form has been returned. A copy of the signed informed consent will be given or sent to the study participant. The consent form will be retained as part of the study records. The informed consent process will be documented in the patient file and any discrepancy to the process described in the protocol will be explained.

The links with the study information to the online surveys are sent to the women by the investigator or the research assistant. The online survey will be programmed in REDCap® (Research Electronic Data Capture) and anonymised. It will enable health care providers to consent to or decline participation in the online survey itself.

Recruitment for the individual interviews with the birth attendant midwives in the Canton Hospital Winterthur will be conducted via the research assistant or the head of midwives.

3.3 Study procedures

The study duration will be one and a half year. The recruitment period will be one year. Participants will be recruited in their second or beginning of third trimester of pregnancy. After

signing the consent form, participants will register for an antenatal education class. Due to the course organisation at the Cantonal Hospital Winterthur, randomisation is conducted at the course level. The randomisation is performed by envelopes with the corresponding information about the course (intervention yes or no). In the randomisation process the sponsor-investigator and local project leader will be excluded.

Prior to the start of the classes, the participants fill in the online baseline questionnaire, which was sent to them by email. After the antenatal class, at around 36 weeks of gestation, the participants complete the education online questionnaire. The study assistant transfers the birth data anonymously directly from the clinic system to REDCap®. Finally, the postpartum online questionnaire is completed within four weeks after the birth (see Figure 1).

[figure not shown]

Figure 5 Study process

The following table provides an overview on the study instruments and the timing of their application for data collection:

Table 1 Study instruments and timing of application

Questionnaires / Interview	Time of application	Content	Filled in by
Baseline questionnaire (T0)	After recruitment before the antenatal education class started	Socio-demographic data, medical and obstetric history, German versions of the Childbirth-Self-Efficacy Inventory	Participant
Education questionnaire (T1)	After intervention (around 36 weeks of gestation)	Data about the antenatal education class, German versions of the Childbirth-Self-Efficacy Inventory	Participant
Labour and birth questionnaire (T2)	After birth	Labour and birth outcomes for mother and child, early postpartum period	Research assistant
Postnatal questionnaire (T3)	Early postnatal questionnaire (within 4 weeks after birth)	German version of the Childbirth experience questionnaire, postnatal quality of life, Data about the antenatal education class	Participant
Semi-structured interview guide	After birth (within 10 working days)	Women's experience during birth, feasibility of the breathing and relaxation technique learned, self-efficacy and self-confidence observed	Research assistant and birth attendant midwives

3.3.1 Potential bias and measures, to reduce them:

Sociodemographic questions as well as the validated questionnaires (German versions of the Childbirth-Self-Efficacy Inventory (Schmidt et al., 2016)) used for the validation of the antenatal education class will be applied before giving birth. To reduce the workload for the women, the study assistant transfers important information about the labour and birth directly from the medical birth report into the data entry tool. It is not possible to blind the midwives who conduct the antenatal education classes. However, after consent, the women are randomized and assigned to a class accordingly. In addition, the collected data will be entered by a research assistant, to ensure that data entry and data analysis are carried out by different people.

Study dropouts and possible loss to follow-up are part of research projects. For this reason, an intention-to-treat principle is conducted to minimize attrition bias.

Women after childbirth might evaluate their birth experience too optimistically. This could bias their satisfaction with the skilled breathing and relaxation technique and the attended antenatal education class. Beside questions about the antenatal education class, we will use a validated

questionnaire to assess labour and birth experience such as the childbirth experience questionnaire (Pedersen et al., 2021) to gain a more comprehensive insight. Additionally, we will use multivariable regression models to estimate the independent effect of the antenatal education class.

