4 STATISTICS AND METHODOLOGY

4.1 Statistical analysis plan and sample size calculation

The socio-demographic and obstetric characteristics will be described employing descriptive statistics including frequency and percentage, mean and standard deviation, median and percentiles. The primary outcomes and secondary maternal and neonatal variables like women's satisfaction with their childbirth experience, self-confidence, pain management, mobility during labour, duration of labour, bonding, 5-minute Apgar-Score and umbilical cord pH will be compared between the study groups using repeated-measures ANOVAs and generalized estimating equations and mixed effects models. Quantitative data is analysed using R. The significance level will be two-sided $\alpha = 0.05$.

The sample size in the intervention phase was calculated based on the scores for the variable of childbirth self-efficacy using G-Power software. Based on the randomised controlled trial of a self-efficacy enhancing educational programme (SEEEP) by Ip et al., (2009). This study reported an effect size of 0.78 in increasing self-efficacy in labour and an attrition rate of around 30.7%. In the proposed study, we therefore assume an overall moderate effect size of 0.75. Setting a power at 80%, a significance level of $p < .05$, a sample size of 29 per arm is needed for a two-arm repeated measures design (GPower, version 3.1). Assuming an attrition rate of 20%, the final sample size will be 35 in each arm and 70 participants in total.

The qualitative data collected from the attendant birth midwives will be conducted by a semi-structured interview guide. The data will be transcribed verbatim and analysed using content analysis (Kuckartz & Rädiker, 2022). The total target sample size for the individual interviews with midwives is 12-15. Variation enriches the results and can be achieved with 12 to 15 interviews. This is important to provide a good basis for the evaluation of the antenatal education class and the feasibility as well as the practicability of the skilled breathing and relaxation technique. Qualitative data will be analysed using MAXQDA. Any deviation from the original statistical plan will be described and justified in the final trial report.

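### Sections 3.3 and 3.3.1 name different units of randomisation (course, woman), and Section 4.1 allows for course in neither the sample size nor the analysis

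*Combined protocol and SAP*

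**What the plan says.** All references are to the combined protocol and SAP.

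- **Section 3.3:** "Due to the course organisation at the Cantonal Hospital Winterthur, randomisation is conducted at the course level". On the mechanism: "The randomisation is performed by envelopes with the corresponding information about the course (intervention yes or no"). Women consent and then register for a class. The text does not say whether a course's status is already known when they register.
- **Section 3.3.1:** "after consent, the women are randomized and assigned to a class accordingly".
- **Section 2.4:** "The women and their partners will be randomly assigned to one of two groups". This also reads as individual assignment, though loosely worded.
- **Section 2.3** describes a two-arm parallel randomised trial and does not mention clusters. Both arms are group classes.
- **Section 2.4, on the intended mechanism:** "Women will experience that they can successfully perform the breathing and relaxation techniques and see that similar other can do it, too". It also relies on reassurance from the class instructors.
- **Section 4.1, sample size:** "a sample size of 29 per arm is needed for a two-arm repeated measures design (GPower, version 3.1"). It continues: "Assuming an attrition rate of 20%, the final sample size will be 35 in each arm and 70 participants in total". The inputs are an effect size of 0.75, 80% power and a two-sided 5% level.
- **Section 4.1, analysis:** outcomes "will be compared between the study groups using repeated-measures ANOVAs and generalized estimating equations and mixed effects models". Course does not appear as a cluster, random effect or covariate.

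**The concern.** In Section 3.3 a woman's arm follows from her course. In Section 3.3.1 her course follows from her own randomisation. The unit determines the allocation procedure, the error term for the treatment comparison and the power, so a reader cannot tell which trial is being run.

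If courses are randomised, the precision of the comparison depends on how many courses there are and how alike women in one course are. A calculation for independent women does not address either.

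Choosing individual randomisation does not remove the issue. Women still share a class and an instructor in both arms. In the BreLax arm, watching peers succeed and hearing the instructor's encouragement are meant to raise self-efficacy, the primary outcome, and both are shared within a class. If outcomes are correlated within a class, an analysis that leaves course out gives standard errors that are too small and a false-positive rate above 5%.

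**Working it through.** **1. Reproducing the plan's figure.** Two-sample t-test, d = 0.75, two-sided 0.05, 80% power, independent women: n = 28.9, so 29 per arm (exact power 80.1%). This matches Section 4.1. The figure therefore contains no clustering allowance.

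**2. Completers.** With the 20% attrition of Section 4.1, 35 × 0.8 = 28 per arm. With the roughly 10% of Section 4.2, 35 × 0.9 = 31.5, taken as 31. Unclustered power is 78.7% for 28 and 82.8% for 31.

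**3. Assumptions the documents do not supply.** Completers per course m = 4 (7 courses per arm) or m = 7 (4 courses per arm); ICC 0 to 0.10; correlation r between baseline (T0) and later self-efficacy of 0.5, varied to 0.3 and 0.7, with the same residual ICC.

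**4. Formulas.** Design effect = 1 + (m − 1) × ICC. At ICC 0.10 this is 1 + 3 × 0.10 = 1.30 for m = 4 and 1 + 6 × 0.10 = 1.60 for m = 7. Effective n = n / design effect. Course-level power uses the noncentral t with degrees of freedom = total courses − 2, that is 14 − 2 = 12 or 8 − 2 = 6. Adjustment for T0 replaces d by d/√(1 − r²); with r = 0.5, 0.75/√0.75 = 0.866.

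**5. Course-level power, 28 completers per arm.**

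| ICC | m = 4, post-only | m = 7, post-only | m = 4, T0-adjusted (r = 0.5) | m = 7, T0-adjusted (r = 0.5) |
|---|---|---|---|---|
| 0 | 73% | 65% | 84% | 77% |
| 0.01 | 72% | 63% | 83% | 75% |
| 0.05 | 67% | 54% | 79% | 66% |
| 0.10 | 62% | 46% | 74% | 57% |

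Unclustered comparators are 78.7% post-only and 88.9% T0-adjusted. The fall at ICC 0 (78.7% to 73% or 65%) is the cost of few degrees of freedom, not of correlation. ICC 0.10 costs a further 11 or 19 points post-only.

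**6. Sensitivity.**
- T0-adjusted power over ICC 0 to 0.10 runs from 77% to 66% (m = 4) and 69% to 50% (m = 7) at r = 0.3. At r = 0.7 it runs from 95% to 89% and 90% to 74%.
- With 31 completers per arm in the same number of courses, post-only power runs from 77% to 65% (7 courses per arm) and 69% to 48% (4 per arm). T0-adjusted at r = 0.5, it runs from 88% to 77% and 81% to 60%.

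**7. Type I error if course is ignored** (t-test on 2n − 2 degrees of freedom, 28 per arm, 200,000 simulated trials per cell):

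| ICC | m = 4 | m = 7 |
|---|---|---|
| 0.01 | 5.3% | 5.7% |
| 0.05 | 6.8% | 8.7% |
| 0.10 | 8.6% | 12.3% |

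A course-level t-test held 4.9% to 5.1% throughout. These rates apply equally to individually randomised women taught in arm-specific classes, if the ICC is the same in both arms.

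**The case against.** - **Section 3.3 may simply be the operative text.** It names the unit, the reason and the envelope content, whereas the sentence in 3.3.1 sits in a paragraph about blinding. The study-process figure is not available here and might show the order of allocation. This makes course randomisation the likelier intent, but the two sentences still conflict, and it is the reading under which the stated power fails to follow.
- **GEE and mixed models can carry a course effect,** and Section 3.3.1 adds multivariable regression. That is right: the plan leaves course unspecified rather than excluding it. However, nothing commits the sponsor to it, and in a repeated-measures plan these models are naturally read as handling correlation within a woman. The type I errors above describe an analysis that omits course, not one the plan names.
- **The t-test origin of 29 is inferred.** Section 4.1 speaks of a repeated-measures design, and a between-group repeated-measures ANOVA (f = 0.375, two measures) also gives 58 in total if the correlation is about 0.95 or more. Either route assumes independent women, so the point is unaffected.
- **The figures rest on assumed course sizes, and smaller courses shrink the problem.** This stands. With 2 completers per course (14 courses per arm), course-level power over ICC 0 to 0.10 is 77% to 73% post-only and 88% to 85% T0-adjusted (r = 0.5), and type I error with course ignored is only about 6% at ICC 0.10. It limits any claim about size, but not the finding that unit, sample size and model do not match.

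**Conclusion.** The concern holds and must be fixed. The textual conflict and the absence of any course allowance in Section 4.1 need no assumed figure. If courses are randomised, the stated 80% power is not supported by the calculation given. Under either unit, leaving course out is anti-conservative to a degree set by the ICC and course size.

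The size is not known. At ICC 0.01 the inflation of type I error is negligible; at ICC 0.10 with 7 completers per course it would be more than double the nominal 5%. Adjusting for T0 may bring power back above 80% or may not, depending on the baseline correlation and the number of courses. It is not established that the trial is underpowered. The documents do not allow the check. Confidence is high for the mismatch; the numerical results are illustrations only.

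**What to change.** 1. **Reconcile the unit.** State one unit of randomisation in Sections 3.3 and 3.3.1, align Sections 2.3 and 2.4 with it, and say whether the course envelope is opened before or after women register.
2. **Record course and name the model.** Hold a course identifier for every woman. Specify one primary model for self-efficacy that adjusts for T0 and accounts for course with a small-sample correction: a random course intercept with Kenward-Roger or Satterthwaite degrees of freedom, or a course-level analysis. If GEE clustered on course is preferred, use a corrected variance; in the same simulations the uncorrected sandwich gave about 9% (7 courses per arm) to 14% (4 per arm) type I error. If the woman is the unit, keep the course term, since both arms are taught in groups.
3. **Restate power or the detectable effect for 70 women,** using the planned number and size of courses, a range of ICCs and one attrition rate (Section 4.1 uses 20%, Section 4.2 about 10%).

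The cost is protocol and SAP wording, a course field in REDCap (Section 3.3 lists only general data about the class) and one extra model term in R. The downside is fewer degrees of freedom and probably a less favourable stated power. The fix itself requires no additional enrolment.
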